Use of Extended Platelet-Rich Fibrin Membranes in Comparison to Collagen Membranes for Socket Grafting: Part 2: A Randomized Clinical Trial

Unique Protocol ID: 13180-[name]

Date of Document: 2/2/2025

Principal Investigator: [name]

Brief Title: E-PRF vs Collagen Membranes in Ridge Preservation

Secondary IDs: None

Statistical analysis Plan for evolution Part 2 study:

The sample size was determined based on the expected mean difference in horizontal ridge width (HRW) between independent groups. A mean difference of 2.3 mm with an estimated standard deviation (SD) of 1.1 mm was used for the calculation. To detect a statistically significant difference at an α level of 0.05 with 90% power, a minimum of 11 participants per group was required. Considering an anticipated 20% dropout rate, the final target sample size was set at 14 participants per group.

All statistical analyses were conducted using GraphPad Prism version 10.0 (GraphPad Software, San Diego, CA, USA). Data were first evaluated for normality utilizing the Shapiro-Wilk test. One-way analysis of variance (ANOVA) was used to identify overall differences among the research groups. When ANOVA showed statistical significance, appropriate post hoc tests were performed. Tukey's multiple comparison test was used to compare all possible pairs of group means in the study, where no single control group was defined (i.e., membranes' fabrication and application time). In contrast, Dunnett's post hoc test was used in the analysis involving a defined control group (i.e., collagen) to specifically compare test groups with the control group while controlling for type I error across multiple comparisons. Results were expressed as mean \pm standard deviation (SD), and statistical significance was set at $p < 0.05$.

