This study will undertake a comprehensive analysis to compare outcomes across 5 distinct treatment groups. The primary focus will be to evaluate differences in ridge dimensions through dental radiology and also to evaluate soft tissue healing and closure at 2 weeks post-operatively. The goal is to draw conclusive findings regarding the healing of extraction sites, soft tissue thickness, and ridge dimensions.

Compensation to Participants

Participants will not receive any type of compensation or payment for their participation in the study.

Adverse Event Reporting

In the case of an adverse event (AE) or severe adverse event (SAE) directly associated with the study, participants will not be financially responsible for any consequences resulting from their participation in the study. Should a serious AE occur, any associated medical expenses or required interventions will be covered by the research team. The investigators are fully committed to providing support and resources to manage and address any unexpected challenges that may arise, reaffirming the investigators commitment to the ethical and responsible conduct of research.

Adverse event reporting aims to ensure participant safety, facilitate the evaluation of the intervention's safety profile, and contribute to the overall understanding of potential risks associated with blood draws and extraction and implant therapy. When an adverse event (AE) or severe adverse event (SAE) occurs, it will be promptly and accurately documented. The AE or SAE will be classified in nature, severity and relation to the procedure. It will be reported to all parties including the regulatory authority and ethics committee. The subject will be closely followed until the AE or SAE has been resolved. Timely and transparent reporting is essential for maintaining the integrity of the study, protecting participant welfare, and informing regulatory decisions to ensure the ongoing safety and efficacy of medical interventions.

Principle Investigator Safety Monitoring

1.) Adverse Event Monitoring:

- a. Evaluation of any adverse events (AEs) or serious adverse events (SAEs), which are unfavorable or unintended medical occurrences, to determine their nature, severity, and relationship to the intervention.

2.) Data Collection and Analysis:

- a. Continuous collection and analysis of safety-related data including participant health status and reported symptoms, to identify any patterns or trends that may indicate safety concerns.

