Patients will be seen 2 weeks after each procedure to ensure proper healing and any adverse reactions will be recorded. Intra-oral photographs will also be taken at each visit to evaluate wound

healing. 3-months after ridge preservation, patient will be seen for a radiographic evaluation (CBCT) for proper implant planning.

Re-evaluation treatment (not required)

Patients will be encouraged to return every 6 months after the surgery for data collection including probing depths.

Periodontal Maintenance Treatment

Patients will be placed on a 6-month maintenance with data collection (periodontal charting and fasting blood draw) occurring at each maintenance for up to 1-year after implant placement. Patients will also have supragingival scaling completed with curettes and ultrasonic device completed by a trained study personnel. The first maintenance will begin 6 months after the implant uncovering surgery visit until the 1-year follow-up conclusion of the study. The total study from extraction to final follow-up may last up to 2-years.

Study Timeline

Visit 1 - Screening/Baseline

- Informed Consent
- Medical History
- HIPPA Form
- Urine HCG test if applicable
- Inclusion/Exclusion Criteria
- Periodontal charting
- Necessary Radiographs (CBCT)
- Soft tissue measurements
- Intra-oral photographs

Visit 2- Treatment

- Treatment (Extraction Procedure)
- Intra-oral photographs
- Soft tissue measurement
- Necessary radiographs (CBCT)

Visit 3- Post-operative visit

- 2-week post-operative evaluation after surgical procedure.
- Intraoral photographs

Visit 4- Implant planning appointment

- Necessary Radiographs (CBCT)

Visit 5- Treatment

- Treatment (Implant placement)
- Soft tissue measurements
- Intraoral photographs
- Peri-apical radiographs

Visit 6- Post-operative visit

- 2-week post-operative evaluation after surgical procedure.
- Intraoral photographs

Visit 7- Treatment

- Treatment (implant uncovering appointment)
- Necessary radiographs (CBCT)
- Intraoral photographs

Visit 8- Post-operative visit

- 2-week post-operative evaluation after surgical procedure.

Visit 9 (encouraged)- periodontal maintenance (6 months after implant uncovering)

- Supragingival scaling
- Complete periodontal charting
- Necessary radiographs (CBCT)

Visit 10 (encouraged)- periodontal maintenance (12 months after implant uncovering)

- Supragingival scaling
- Complete periodontal charting
- Necessary radiographs (CBCT)

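### The SAP leaves horizontal ridge width undefined as to scale, visit and level, and analyses it by one-way ANOVA with no baseline term, forgoing a cheap gain in precision from a scan already scheduled at Visit 1

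*SAP*

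**What the plan says.** The SAP sizes the trial on HRW: "A mean difference of 2.3 mm with an estimated standard deviation (SD) of 1.1 mm was used for the calculation". It gives no visit or ridge level, and does not say whether the 1.1 mm is the SD of a final width or of a change. The analysis is "One-way analysis of variance (ANOVA) was used to identify overall differences among the research groups", followed by a conditional step: "When ANOVA showed statistical significance, appropriate post hoc tests were performed". Dunnett is used against collagen, and Tukey where there is no control group (fabrication and application time). No covariate is named. The text is in the past tense and names one package: "All statistical analyses were conducted using GraphPad Prism version 10.0".

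The protocol does not use the term HRW. Under Data Analysis and Interpretation it says "The primary focus will be to evaluate differences in ridge dimensions through dental radiology", without scale or visit. Project Design describes a 6-month trial. In the Study Timeline, "Visit 1 - Screening/Baseline" precedes the extraction at Visit 2 and lists both "Necessary Radiographs (CBCT" and "Soft tissue measurements". CBCT appears again at Visits 2, 4, 7, 9 and 10, and soft tissue measurement at Visits 2 and 5. The Methods section also places a radiographic record at the end of surgery.

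**The concern.** There are two linked gaps.

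First, the outcome that sized the trial is not pinned down. The 3-month scan (Visit 4) and the scan at implant uncovering (Visit 7, which follows implant placement) are both candidates. Either could be analysed as a width or as a change, and change could be taken from Visit 1 or from the end-of-surgery scan. A reader cannot tell which number will be the result, and the choice could be made after seeing the data.

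Second, a pre-treatment measurement is scheduled but not used. If final width is analysed, variation explained by starting width stays in the error term. If change is analysed, baseline is subtracted with its coefficient fixed at 1. That over-corrects a chance imbalance whenever the true slope of follow-up on baseline is below 1. In both cases what is at stake is precision, and its size depends on the definition that is missing.

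**Working it through.** **Inputs from the SAP.** Difference 2.3 mm; SD 1.1 mm; 11 evaluable per group; 14 after 20% dropout. From the protocol: five groups, so four comparisons with collagen; 80-100 enrolled.

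**Assumptions not in the documents.** Baseline to follow-up correlation r = 0 to 0.8; equal variances at the two times, except in step 4; illustrative differences of 1.0 and 1.5 mm; equal allocation.

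**1. The plan's own figure.** Two independent means with the stated inputs need 5 per group (normal approximation) or 6 (exact t), two-sided, so the 11 does not reproduce. The inflation does: 11/0.8 = 13.75, rounded up to 14. The shortfall in reproduction is a separate matter. Here it means only that 11 per group is ample for 2.3 mm.

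**2. Unadjusted precision and power at 11 per arm.** The two-sided Dunnett critical value (four comparisons, 50 df) is 2.522.
- Half-width = 2.522 × 1.1 × √(2/11) = 1.183 mm.
- The standard error of a difference is 1.1 × √(2/11) = 0.469 mm. Noncentral-t power, without the ANOVA gate, is 0.357 for 1.0 mm, 0.748 for 1.5 mm and 0.990 for 2.3 mm.
- With the SAP's gate (simulated, 20,000 five-arm trials per cell), power is 0.31-0.33 for 1.0 mm, 0.72-0.74 for 1.5 mm and 0.99 for 2.3 mm.

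**3. With Visit 1 HRW as covariate, 11 per arm.** The critical value is 2.524 (49 df). Half-width = 2.524 × 1.1 × √(2/11) × √ratio. The ratio is 1 − r² if 1.1 mm is the SD of final width, and (1 + r)/2 if it is the SD of change from Visit 1. Power below is for 1.0 mm, without the gate.

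| r | Final: ratio | Half-width (mm) | Power | Change: ratio | Half-width (mm) | Power |
|---|---|---|---|---|---|---|
| 0 | 1.00 | 1.184 | 0.357 | 0.50 | 0.837 | 0.688 |
| 0.3 | 0.91 | 1.129 | 0.395 | 0.65 | 0.954 | 0.552 |
| 0.5 | 0.75 | 1.025 | 0.481 | 0.75 | 1.025 | 0.481 |
| 0.7 | 0.51 | 0.845 | 0.677 | 0.85 | 1.091 | 0.424 |
| 0.8 | 0.36 | 0.710 | 0.844 | 0.90 | 1.123 | 0.399 |

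The gain grows with r on one reading and shrinks with r on the other. At 14 per arm the unadjusted half-width is 1.041 mm; adjusted, it runs from 1.041 to 0.625 mm (final) or 0.736 to 0.988 mm (change).

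**4. Unequal variances, change reading.** Let k = SD(follow-up)/SD(baseline). The variance of ANCOVA relative to change-score ANOVA is k²(1 − r²)/(k² + 1 − 2rk). At r = 0.8 and k = 1.25 this is 1.5625 × 0.36/(1.5625 + 1 − 2.0) = 0.5625/0.5625 = 1.00. The slope rk is then 1 and nothing is gained.

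**5. Protocol enrolment.** 80/5 = 16 and 100/5 = 20 per arm are enrolled numbers. After 20% dropout they become 12.8 (about 13) and 16 evaluable. Unadjusted, ungated power for 1.5 mm is then about 83% to 91%, against 75% at 11.

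**6. Missing baselines.** As an illustration with an assumed rate (final reading, r = 0.5, 11 per arm, 20% missing completely at random, simulated), dropping those participants gives a half-width of 1.17 mm and loses the gain. Mean imputation of baseline gives 1.06 mm.

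**The case against.** The strongest reply is that the covariate is optional. Randomisation makes unadjusted ANOVA a fair comparison, power for the planned 2.3 mm is already about 99%, and r is not documented. On the final-width reading the gain is nil at r = 0; on the change reading it can be nil when follow-up is more variable than baseline. The change figures also do not apply if change is measured from the end-of-surgery scan, because they assume that the covariate is the same baseline that was subtracted. All of this stands, and it limits the point to precision for intervals and for differences below 2.3 mm.

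A reader might infer that omitting baseline biases the comparison or invalidates the test. The documents do not support this: allocation is randomised, and the omission leaves type I error intact. A reader might also infer that the trial is underpowered without adjustment; step 2 shows that it is not, for the effect it was sized on.

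A further tempting inference is that many participants will lack a baseline scan. The protocol's Regular Assessments items put an assessment at each visit and a CBCT at each assessment visit, and the Visit 1 list includes CBCT. Only the qualifier *necessary* in that list leaves some doubt. A missing-baseline rule is therefore a precaution and does not answer a demonstrated gap.

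**Conclusion.** The point holds as a recommended improvement. The SAP leaves the scale, visit and ridge level of HRW open and names no baseline term, although a pre-treatment measurement is scheduled. With 11 evaluable per arm, equal variances and r from 0 to 0.8, adjustment takes the Dunnett 95% half-width from 1.18 mm to between 1.18 and 0.71 mm (SD of final width) or between 0.84 and 1.12 mm (SD of change from Visit 1). Ungated power for a 1.0 mm difference goes from 36% to between 36% and 84%, or between 69% and 40%, in the same order of r. These ranges are conditional: r and the variance ratio are not in the documents, and the calculation takes one independent site per participant. The missing definition is the weightier half, because it decides which range applies and leaves the choice of result open.

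**What to change.** - Define HRW as follow-up width at one named visit (for example the 3-month CBCT at Visit 4) and one named measurement level.
- Analyse it with a linear model containing treatment group and HRW at the same level on the Visit 1 CBCT. The end-of-surgery scan should not be the covariate, because it is taken after the assigned membrane and graft are in place.
- Report Dunnett-adjusted contrasts of adjusted means against collagen. State whether the overall-test gate is kept; if so, use the group F test from this model.
- Keep participants with a missing baseline, using a simple imputation that ignores arm and outcome.
- If soft tissue thickness is analysed, adjust it for its Visit 1 value at the same aspect (buccal and lingual separately, or a stated average).
- Leave fabrication and application time, which have no baseline, in one-way ANOVA with Tukey.
- Because the SAP is in the past tense, state whether results had been seen. If they had, label as post hoc both the adjusted analysis and the choice of visit, scale and level.

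The cost is SAP wording, one error degree of freedom (1.183 to 1.184 mm at r = 0 by formula, 1.18 to 1.19 mm in simulation), measurement of HRW on scans already scheduled, and possibly a different package for Dunnett contrasts of adjusted means. No extra scan, visit or participant is needed.

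### Dunnett's comparisons with collagen are run only after a significant ANOVA, a gate that Dunnett does not need: it makes the test conservative and costs some power, mainly for effects below the planned 2.3 mm

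*SAP*

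**What the plan says.** The statistical analysis paragraph of the SAP sets out a two-step procedure. First, "One-way analysis of variance (ANOVA) was used to identify overall differences among the research groups". Second, "When ANOVA showed statistical significance, appropriate post hoc tests were performed".

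Two post hoc tests are then named. Tukey is for analyses "where no single control group was defined (i.e., membranes' fabrication and application time"). Dunnett is for analyses with collagen as control, and its stated purpose is "to specifically compare test groups with the control group while controlling for type I error across multiple comparisons". The significance level is 0.05; sidedness is not given.

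The SAP gives no reason for the ANOVA step, does not account for it in the sample size, and does not say that Dunnett's results will be reported if the ANOVA is not significant. The gate is not limited to any one outcome. The protocol (Interventions) defines five groups, one collagen and four e-PRF.

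**The concern.** By the SAP's own account, the protection against multiple testing comes from Dunnett. Dunnett's critical value is derived so that the chance of any false claim among the four comparisons with collagen is 5%, whether or not an F test has been done. Requiring a significant F test as well means that a trial must pass two tests to name an arm. The second condition can turn a Dunnett-significant result into no result, and never the reverse.

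The F test also has 4 degrees of freedom, so it spreads its power over all contrasts among five means, including those between e-PRF arms. When the four e-PRF arms behave alike, or most lie between collagen and the best arm, the F test can miss a difference from collagen that Dunnett would find. Four versions of one product could plausibly behave alike. At stake is a real difference from collagen going unnamed although it meets the multiplicity-adjusted 5% criterion.

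**Working it through.** **Inputs.** Five groups (protocol, Interventions). SD 1.1 mm, planning difference 2.3 mm, α 0.05, minimum 11 and target 14 per group (SAP, sample-size paragraph). Total enrolment 80–100 (protocol, Enrollment), which is 16–20 per arm if equal. Assumed: two-sided tests, equal arms, normal data, common SD.

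**The SAP's own figure.** "To detect a statistically significant difference at an α level of 0.05 with 90% power, a minimum of 11 participants per group was required". A plain two-sample formula gives n = 2(1.960 + 1.282)² × (1.1/2.3)² = 2 × 10.51 × 0.2287 = 4.8, so 5 per group, or 6 with the t distribution. The 11 therefore does not follow from the stated inputs alone. The dropout step does: 11/0.8 = 13.75, so 14. The unreproduced 11 is a separate matter. I take 11 and 14 as given, since the results below depend little on it.

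**How a trial is blocked.** With n = 11 the pooled degrees of freedom are 5 × 10 = 50. Dunnett's two-sided critical value for four comparisons is about 2.52 (simulated). The 5% critical value of F(4, 50) is 2.56. Suppose the observed SD is 1.1 mm, one e-PRF arm is 1.3 mm from collagen, and the other three lie midway at 0.65 mm.

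- Standard error of a difference: 1.1 × √(2/11) = 0.469 mm.
- Dunnett: t = 1.3/0.469 = 2.77, above 2.52, so significant.
- Squared deviations of the five means from their average sum to 0.5 × 1.3² = 0.845, so their variance is 0.845/4 = 0.211.
- ANOVA: F = 11 × 0.211/1.1² = 1.92, below 2.56, so not significant.

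The multiplicity-adjusted difference from collagen is present, and the SAP's rule does not allow it to be tested.

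**False-positive rate, no true differences** (simulation, 2–4 million runs):

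| Procedure | No gate | With gate |
|---|---|---|
| Dunnett, five groups | 5.0% | 2.8% |
| Tukey, five groups | 5.0% | 4.0% |
| Tukey, four groups | 5.0% | 4.2% |

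The Dunnett figure is 2.8% at n = 11, 14, 16 and 20 alike. If one e-PRF arm differs greatly and three equal collagen, the error on the three true nulls is about 4.0% with or without the gate, because the F test is then always significant.

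**Power to find any e-PRF arm different from collagen**, n = 11 (200,000–400,000 runs per point):

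| True pattern | No gate | With gate | Loss (points) |
|---|---|---|---|
| All four at 0.8 mm | 46% | 33% | 13 |
| All four at 0.9 mm | 56% | 42% | 14 |
| All four at 1.0 mm | 65% | 51% | 14 |
| All four at 1.2 mm | 81% | 69% | 12 |
| One at 1.2, three at 0.6 mm | 56% | 44% | 12 |
| Only one, at 1.2 mm | 54% | 50% | 3 |
| One at 2.3, three at 1.15 mm | 99.1% | 97.6% | 1.5 |
| All four at 2.3 mm | 99.98% | 99.92% | 0.06 |

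Losses are taken from unrounded figures.

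**Power for one given arm**, n = 11:

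- All four at 1.0 mm: 35.7% to 31.8%, a loss of about 4 points.
- Only that arm shifted, 1.2 mm: 52.0% to 48.7%, about 3 points.
- Graded effects (that arm at 1.1 mm, the others at a quarter, half and three quarters of it): a loss of about 6 points.
- Other three midway, that arm at 1.3 mm: 60% to 50%, about 10 points.

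**Larger arms.** With all four at 1.0 mm, n = 14 gives 76% to 64%. The peak loss at n = 14 is still about 14 points, at 0.8 mm (57% to 43%). At n = 20 the loss is about 8 points at 1.0 mm, 3.0 at 1.2 mm and 0.3 at 1.5 mm. Adding participants moves the peak to smaller effects.

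**The case against.** The strongest reply is that the rule is conventional and safe. It creates no false positives, and at the 2.3 mm on which the trial was planned it costs almost nothing: under 0.1 point if one arm or all four are shifted, and 1.5 points (0.3 at n = 14) if the other arms lie midway. The 14 points needs three things together: all four arms shifted equally, by less than half the planned effect, and success counted as finding any arm. With 80–100 enrolled, the peak moves to still smaller effects. All of this stands, and it limits the size of the point.

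It can also be said that a five-group F test fits the protocol, whose stated gap covers differences between the four e-PRF iterations as well as the comparison with collagen. That is right: the F test is not off-question for the trial as a whole. It is still an unnecessary precondition for the collagen comparisons.

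The SAP is written in the past tense. If outcome data have already been seen, lifting the gate would be a post hoc change. The documents do not settle this, so it bears on how the fix is made and not on whether the gate is needed.

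What the reply does not answer is that 2.3 mm is a planning value for horizontal ridge width only. The protocol also lists soft tissue thickness, healing quality and implant success in its primary objective. No effect size is planned for these, and the gate covers whichever outcomes go through the ANOVA.

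**Conclusion.** The point holds as a modest efficiency defect. The gate is in the SAP, Dunnett does not need it, and removing it keeps the family-wise error at 5%. Its cost is at most about 14 points of power for any difference from collagen, about 3 to 10 points for a given arm in the patterns tried, and at most about 1.5 points at 2.3 mm. These figures assume two-sided tests, five equal arms, normal data, a common SD of 1.1 mm and 11 analysed per arm.

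Four stronger readings are tempting and are not supported:

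- That the whole procedure runs at 2.8%. This figure is Dunnett's, and only when no arm differs. Gated Tukey is at about 4.0%, and the SAP names Tukey only for fabrication and application time.
- That the gate makes the error rate invalid. It is conservative.
- That the trial as planned loses 14 points. That is a worst case well below the planned effect.
- That a non-significant ANOVA will be reported as no difference. The SAP does not say how it will be reported; it says only that the post hoc tests follow significance.

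**What to change.** Replace the sentence that makes the post hoc tests conditional with: *Dunnett's test of each e-PRF arm against collagen (and Tukey's test where all pairs are of interest) is performed and reported whatever the ANOVA result; the ANOVA F test is descriptive.*

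Make the change before outcome data are examined, and date it. If data have already been examined, report the gated result as specified and label the ungated Dunnett results as a post hoc change.

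The cost is one SAP sentence. No further participants, measurements or visits are needed, and the family-wise error for the collagen comparisons is 5%, the level that the SAP declares.

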Use of Extended Platelet-Rich Fibrin Membranes in Comparison to Collagen Membranes for Socket Grafting: Part 2: A Randomized Clinical Trial

Unique Protocol ID: 13180-[name]

Date of Document: 2/2/2025

Principal Investigator: [name]

Brief Title: E-PRF vs Collagen Membranes in Ridge Preservation

Secondary IDs: None

Study Protocol:

Abstract

Dental implants are often considered the gold standard to replace missing teeth. Having success with dental implants depends on the hard tissue and soft tissue remaining after tooth extractions. The first step to successful dental implant placement begins with proper socket grafting which includes placing a bone graft and membrane among other biomaterials such as platelet-rich fibrin (PRF) to prevent the collapse of the ridge that occurs after a dental extraction.

While platelet-rich fibrin is commonly utilized for ridge preservation, it is often used in conjunction with a collagen membrane due to the fact that it has a short resorption time lasting roughly 2 weeks. However, recently, it was discovered that by heating the plasma layer and denaturing the albumin, the resorption properties of PRF could be extended from 2 weeks to 4-6 months. This extended platelet-rich fibrin (e-PRF) membrane is a promising replacement to collagen membranes in various surgeries. The investigators previously demonstrated that it is a safe and feasible alternative to conventional membranes with 4 different iterations of applying the novel e-PRF membrane. However, there still lacks a comparative study to traditional collagen membranes and between the 4 different iterations.

Objective

The purpose of this study is to evaluate and compare the effectiveness of 4 different iterations of utilizing e-PRF membranes with a collagen resorbable membrane. Each placement will receive either one of the 4 different variations of e-PRF membranes or a collagen resorbable membrane in alveolar ridge augmentation.

Project Design

This research will be a 6-month randomized and controlled trial involving patients requiring at least one extraction and replacement with a dental implant. Participants will be recruited and randomly allocated to receive either one of the four iterations of using e-PRF membranes or a standard resorbable collagen membrane. All patients will be treated surgically with ridge preservation and dental implant placement using standard bone graft material and one of the membranes determined by their assigned group.

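### Naming step-down Dunnett for the four comparisons with collagen would keep the 5% family-wise error and lose no rejection, for a modest gain in power if true differences fall below 2.3 mm

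*SAP*

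**What the plan says.** The protocol's Objective is to "evaluate and compare the effectiveness of 4 different iterations of utilizing e-PRF membranes with a collagen resorbable membrane". Its Interventions section lists collagen as the control and four e-PRF groups, so there are four comparisons with one control.

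The SAP's analysis paragraph begins with a one-way ANOVA: "When ANOVA showed statistical significance, appropriate post hoc tests were performed". For the comparisons with collagen, "Dunnett's post hoc test was used in the analysis involving a defined control group (i.e., collagen", and the purpose is "to specifically compare test groups with the control group while controlling for type I error across multiple comparisons". Significance is set at p < 0.05. Results are to be given as mean and SD, and no simultaneous confidence intervals are planned. The SAP does not say whether Dunnett's test is single-step or step-down.

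The sample-size paragraph states: "A mean difference of 2.3 mm with an estimated standard deviation (SD) of 1.1 mm was used for the calculation". It continues: "at an α level of 0.05 with 90% power, a minimum of 11 participants per group was required".

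**The concern.** Single-step Dunnett holds every arm to the critical value for four comparisons, even after other arms have been declared different from collagen. Once an arm has been rejected, fewer true nulls can remain, so part of the 5% allowance goes unused. Step-down Dunnett spends it by lowering the critical value at each step.

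The Objective asks about each of four iterations, so power beyond the first rejection matters. What is at stake is that an iteration that truly differs from collagen could be reported as not significant when a test with the same error guarantee, on the same data, would have shown the difference. The usual reason to stay with the single-step form is that it comes with simple simultaneous intervals, and this SAP does not plan any.

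**Working it through.** **Inputs.** From the SAP: SD 1.1 mm, planning difference 2.3 mm, α 0.05, 11 analysed per group, 20% dropout, 14 per group enrolled. From the protocol: five groups, and 80–100 subjects under Enrollment. Assumed: single-step reading of Dunnett, two-sided tests, equal group sizes, normal data, and every true difference other than 2.3 mm.

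**The plan's own figure.** For two groups, n = 2(z₀.₉₇₅ + z₀.₉₀)²(SD/difference)² = 2 × (1.960 + 1.282)² × (1.1/2.3)² = 4.8, so 5 per group, or 6 by the exact t-test. The stated 11 is not reproduced. Variants that allow for multiplicity or five groups give 7 to 10, but the SAP names none of them. The dropout step does reproduce: 11/0.8 = 13.75, so 14. The present point does not depend on where 11 came from.

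**The two procedures.** With 11 per group the error term has 5 × (11 − 1) = 50 df, and t = (arm mean − collagen mean) / (s√(2/11)).

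- Single-step: reject each arm with |t| > 2.52.
- Step-down: order the four |t| values, compare them in turn with about 2.52, 2.42, 2.28 and 2.01 (the critical values for 4, 3, 2 and 1 comparisons), and stop at the first failure.

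No later critical value exceeds 2.52, so an arm with |t| > 2.52 is always rejected by step-down too. No rejection was lost in any simulated trial.

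**Family-wise error** (simulation, 11 per arm, no ANOVA step, non-null arms at 2.3 mm). Step-down stays at about 5% under the global null and with two or three arms truly different. Single-step falls to about 2.8% with two arms different and 1.5% with three. That shortfall is the unused allowance.

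**Power** (simulation, 300,000 five-arm trials per scenario, SD 1.1 mm, ANOVA step kept; single-step → step-down):

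| True differences from collagen (mm) | Analysed per arm | Given non-null arm | All non-null arms |
|---|---|---|---|
| 1.5, 1.5, 1.5, 1.5 | 11 | 73% → 80% | 48% → 68% |
| 1.5, 1.5, 1.5, 1.5 | 14 | 86% → 91% | 67% → 83% |
| 1.5, 1.5, 1.5, 1.5 | 16 | 91% → 95% | 77% → 89% |
| 1.5, 1.5, 0, 0 | 11 | 75% → 77% | 62% → 66% |
| 1.5, 0, 0, 0 | 11 | 73% → 73% | 73% → 73% |
| 2.3, 2.3, 2.3, 2.3 | 11 | 99.0% → 99.7% | 97% → 99% |

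Without the ANOVA step, the first row becomes 75% → 82% per arm and 48% → 68% for all four, so the gain does not come from that step. The chance of at least one significant arm is essentially unchanged. It is 88.7% under both forms in the first row.

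The 16-per-arm row covers the upper end of the protocol's enrolment: 80–100 subjects over five arms is 16–20 each, or about 13–16 after 20% dropout.

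**Intervals.** An extra step-down rejection has |t| at or below 2.52, so its single-step 95% interval includes zero. With 11 per arm the standard error is 1.1 × √(2/11) = 0.47 mm, and the interval can reach past zero by up to about (2.52 − 2.01) × 0.47 = 0.24 mm.

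**The case against.** Single-step Dunnett is a correct test for four arms against one control, and it does what the SAP says it is for. At the SAP's planning difference the change makes almost no difference. The scenarios with a visible gain use differences that are not in the documents. Step-down p-values also do not pair cleanly with single-step intervals, and the SAP commits all analyses to one named package, which may not offer the step-down form. All of this stands, and it is why the point is optional.

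A reader might infer that the plan gives up 20 points of power. That is too strong. In the scenarios above, the 20 points are the chance that all four arms are significant at once when all four differ equally by a moderate amount. A similar figure arises for one weak arm when the other three clearly differ: at 11 per arm, with three arms at 2.3 mm and the fourth at 1.1 mm, the power for the fourth goes from 44% to 63%. With four equal differences, the power for a given arm gains at most about 8 points.

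A reader might also infer that the four iterations will move together because they share a material. The documents do not say so. The protocol states that a comparison between the iterations is lacking, and one of them is a gel filler, so equal effects are an assumption.

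Finally, the SAP does not state that it uses the single-step form. That is the normal reading of the unqualified name, not a documented fact.

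**Conclusion.** The point holds as a cheap improvement. It does not show an error. Step-down Dunnett gives the same 5% family-wise guarantee and never loses a rejection. With SD 1.1 mm, 11 analysed per arm and four equal differences of 1.5 mm, it adds about 7 to 8 points of power per arm and about 20 points to the chance of showing all four. The gains shrink to about 4 and 13 points at 16 per arm, and to about 2 points per arm if only two arms differ. They are small at 2.3 mm, and about nil if one arm differs or for the chance of at least one finding. The benefit therefore depends on several iterations truly differing from collagen by less than the planning value, which the documents neither support nor exclude.

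**What to change.** In the SAP's analysis paragraph, name the step-down Dunnett procedure for the comparisons with collagen: order the four |t| values on the common error term, compare them in turn with the Dunnett critical values for 4, 3, 2 and 1 comparisons (about 2.52, 2.42, 2.28 and 2.01 at 50 df), stop at the first failure, and report step-down adjusted p-values. Fix the choice before outcomes are examined. If the single-step form is preferred, the SAP should say so.

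The cost is one sentence and a few lines of code, possibly outside the named software. No extra participants, visits or data are needed. If single-step Dunnett intervals are added, the report must state that any arm significant only by step-down has an interval that includes zero.
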